## **II. Criteria for selecting study participants.**

### **1. Number of participants. (91 patients), will be divided into 3 groups**

1. The first group (n=31) included patients who received enteral nutrition (EN) after surgery.
2. The second group (n=30) included patients receiving parenteral nutrition (PN).
3. The third group (n=30) receiving mixed nutrition (MN), as is commonly considered the method of partial parenteral nutrition, in the early postoperative period.

### **2. Gender distribution**

The study will include both genders.

### **3. Age.**

Age from 20 to 75 years.

### **4. Nationality (ethnicity).**

The racial and ethnic distribution of participants was not significant, so the study included individuals of varying national and ethnic backgrounds.

### **5. Criteria for inclusion.**

- patients or relatives who consented to participate in the study (informed consent).
- patients with concomitant diseases (cardiovascular disease, liver and kidney dysfunction, lung diseases) that may complicate the course of the operation and the postoperative period, or patients who have previously undergone various operations.

### **6. Criteria for exclusion.**

- age up to 20 years, pregnant and lactating
- patients with an unstable condition, unstable hemodynamics or severe concomitant pathology in the acute stage.

### **7. Vulnerable groups.**

The study did not include participants who are considered to be in a vulnerable group.

## **III. Methods and procedures**

Study plan:

- 1) Content analysis of medical documentation.

IV. 2) Obtaining informed consent;

- 3) Biochemical studies: transaminases, thymol test, urea, creatinine, study of total protein and its fraction, state of nitrogen metabolism, blood glucose level, body mass index
- 4) Study of the acid-base state and gas composition of the blood.
- 5) Control of tests before and in the early postoperative period against the background of ongoing nutritional support (determining quantitative ratios of fat mass, water and dry matter in patients before surgery and in the early postoperative period).
- 6) Determination of the immunological state before and after surgery as part of nutritional nutrition.

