## **1. Methods and procedures.**

At the first stage, modern ideas about methods for assessing nutritional status and methods of nutritional support in the early postoperative period of patients operated on for malignant tumors of the hepatopancreatoduodenal zone were studied.

At the second stage, taking into account the need to select the optimal method of nutritional support in the early postoperative period, patients underwent an intragroup and intergroup comparative analysis of the main clinical and laboratory indicators, reflecting the most satisfactory dynamics of plastic processes regarding the type of nutritional support: enteral, parenteral and mixed.

To solve these problems, a prospective, longitudinal, parallel study and retrospective analysis of the results of treatment of 91 patients with malignant tumors of the hepatopancreatoduodenal zone who underwent the following operations were carried out:

- 1) resection of various segments of the liver;
- 2) hemihepatectomy;
- 3) transhepatic drainage of the right and left hepatic duct;
- 4) bypass gastroenteroanastomosis or cholecystoenteroanastomosis with interintestinal enteroenteroanastomosis according to Brown;
- 5) gastro-pancreatoduodenal resection;
- 6) corporecaudal resection of the pancreas with splenectomy.

The study was carried out on the basis of the KGP at the RVC "Multidisciplinary Hospital No. 3 of the city of Karaganda". Venue: intensive care unit.

To identify nutritional deficiencies, there are screening methods recommended by the international clinical nutrition associations ASPEN (American Society for Parenteral and Enteral Nutrition - ASPEN) and ESPEN (European Society for Parenteral and Enteral Nutrition - ESPEN), including questioning patients, using standard anthropometric and laboratory data, which makes it possible to assess nutritional status and the degree of its impairment.

At the first stage, the clinical condition of the patient was assessed using the Nutritional Risk Screening (NRS, 2002), Subjective Global Assessment (SGA) and Nutritional Risk Index (NRI) protocols before surgery and on the 5th, 10th, 15th day after surgery .

A comparative assessment of the clinical effectiveness of the use of types of nutritional nutrition in a complex of therapeutic measures after these operations in the hepatopancreatoduodenal zone was carried out.

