Some nutritional status indicators available for determination at the Oncology Clinic were assessed - body mass index (weight measurements were carried out before surgery, on the 5th, 10th and 15th days), basal metabolic rate (calculated using the Harris-Benedict equation, based on anthropometric data of the patient (gender, age, weight and height).), laboratory parameters: blood hemoglobin, lymphocytes, total protein, serum albumin, serum transferrin, total bilirubin and direct, ALT, AST, which are related to the traditional method for assessing nutritional status.

Additionally, we assessed the duration of postoperative gastostasis, the timing of the onset of intestinal motility, the appearance of stool, the return to a normal diet, the length of patients' stay in the ICU, the readmission of patients to the ICU and the duration of the postoperative bed-day, and the incidence of complications was calculated.

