As can be seen from the presented data, in the preoperative period, according to the SGA assessment, 24 patients in the enteral group, 19 patients in the parenteral group, and 17 patients in the mixed group had normal nutritional status before surgery, with variations relative to patients with moderate to severe malnutrition. Assessment of nutritional status before surgery using the NRI scale allowed us to confirm the nutritional status of the vast majority of patients in all groups as relatively normal

Thus, in 62 of the 91 patients examined, the NRI was assessed as true negative (normal nutritional status), in 26 as true positive (moderate malnutrition), and in 3 as severe malnutrition. Data from the NRI method during this time period had a strong correlation with the results of the SGA scale ( $p < 0.005$ ).

On the 10-12th day of the postoperative period in patients of the “enteral” group, the results of the assessment on the SGA scale remained unchanged; according to the NRI rating scale, there was an increase in “moderate malnutrition” per patient (25%).

With parenteral nutritional support, 17 patients had “normal nutrition”, 14 patients had moderate malnutrition, with regression of “severe malnutrition” in 1 patient. In the mixed nutrition group, there was a complete elimination of signs of “severe malnutrition” by 100% according to the given scales ( $p < 0.005$ ).

In patients of all study groups, throughout the entire period of nutritional support, fluctuations in the level of basal metabolism were observed in average values of  $335.89 \pm 53.6$  kcal/day (13.44%) from the initial value - 1-2 days of the postoperative period and were due to variability body mass index and the dynamics of the temperature curve after surgery.

In patients in the groups with enteral and parenteral nutrition, by the end of these types of energy subsidies (days 10-15), the level of basal metabolism was observed to approach its initial values -  $2500.1 \pm 353.4$  kcal/day and  $2350.0 \pm 330.5$  kcal/day days accordingly. With a mixed type of nutrition, there was a statistically significant decrease in the level of basal metabolism by 6.78% ( $2250.0 \pm 105.2$  kcal/s), which allows us to conclude that patients' energy costs are more effectively covered with this option of nutritional support in a comparative aspect with isolated types nutrition ( $p < 0.03$ ).

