### **Conclusion:**

1. According to the NRI nutritional status assessment scales, the SGA mixed type of nutritional support at the time of transfer of patients to the specialized department and upon completion of this area of intensive therapy in the specialized department by 12-15 days of the postoperative period showed higher effectiveness in stabilizing the condition and maintaining the patients' caloric intake in a comparative aspect with the group of isolated enteral nutrition and parenteral nutrition.
2. Throughout the entire period of isolated enteral, parenteral and mixed nutritional support, all patients (100%) showed a relatively constant level of total blood protein.
3. In patients of all three groups, throughout the entire period of nutritional support, fluctuations in the level of basal metabolism were observed, which was due to the variability of body mass index and the dynamics of the temperature curve after surgery. In patients in the groups with enteral and parenteral nutrition, by the end of nutritional support (days 15-20), the level of basal metabolism was observed to approach its initial values. With a mixed type of nutrition, a statistically significant decrease in the level of basal metabolic rate was observed, which suggests a more effective coverage of the energy costs of patients with this option of replenishing nutritional ingredients.

**Researcher:** [name], PhD student KSMU

[contact].

e-mail: [contact].

[figure not shown]
Signature  17.03.2020

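### Conclusion 3 reads a fall in calculated basal metabolism as better energy coverage, but by the stated equation it is a fall in weight, and the planned fat/water/dry-matter data that could interpret it are not reported

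*Combined protocol and SAP*

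**What the plan says.** **Planned measurement.** Section III (Methods and procedures), study plan item 5, includes "determining quantitative ratios of fat mass, water and dry matter in patients before surgery and in the early postoperative period". It gives no method, device, days or analysis. BMI is listed separately in item 3 of the same plan.

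**Indicators carried forward.** Section III.1 lists "body mass index (weight measurements were carried out before surgery, on the 5th, 10th and 15th days", and a basal metabolic rate "calculated using the Harris-Benedict equation, based on anthropometric data of the patient (gender, age, weight and height". It also lists "blood hemoglobin, lymphocytes, total protein, serum albumin, serum transferrin, total bilirubin and direct, ALT, AST". The Report's Clinical research program repeats this list. Body composition appears in neither.

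**Screening scales.** Section III.1 also uses NRS 2002, "Subjective Global Assessment (SGA) and Nutritional Risk Index (NRI) protocols before surgery and on the 5th, 10th, 15th day after surgery".

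**Analysis.** Neither section III.2 (Data analysis and monitoring) nor the Report's Methods of statistical data analysis mentions fat, water or dry matter.

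**Results and conclusion.** The Report says that changes in basal metabolism "were due to variability body mass index and the dynamics of the temperature curve after surgery". It gives end values of 2500.1, 2350.0 and 2250.0 kcal/day for the enteral, parenteral and mixed arms, the last being a fall of 6.78% (p < 0.03). The results text and Conclusion item 3 both take this fall as a sign that mixed feeding meets energy needs better.

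**The concern.** Objective 3 judges the three feeding methods on nutritional status together with the course of basal metabolism. One of the two conclusions that favour mixed feeding rests on that second element. The quantity is calculated, and its only input that can change over two weeks is weight. After major abdominal surgery weight can change through water, tissue or both, and the meaning for nutrition differs: loss of excess water is neutral, while loss of tissue is unfavourable. Item 5 is the only planned measurement that could tell them apart. Without it, a change in weight is presented as evidence of nutritional benefit.

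**Working it through.** **Step 1. What can move the calculated rate.** The stated inputs are gender, age, weight and height. Over 15 days the first, second and fourth are effectively fixed, so within a patient only weight can change the result. Temperature is not an input. Conclusion item 3 nevertheless describes fluctuation "which was due to the variability of body mass index and the dynamics of the temperature curve after surgery". The BMI part agrees with the equation; the temperature part does not.

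**Step 2. The report's own figures.**
- All arms: 335.89 / 0.1344 = 2499 kcal/day as the implied starting value. The pair is coherent, though that starting value is not stated.
- Mixed arm: 2250.0 / (1 − 0.0678) = 2413.6 kcal/day at the start. The fall is 2413.6 − 2250.0 = 163.6, or about 164 kcal/day.

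**Step 3. Weight change needed for that fall.** The documents do not give the equation's weight coefficients. Assumed: 13.75 kcal/kg for men and 9.56 kcal/kg for women, with a constant multiplier between 1.0 and 1.8.
- Smallest: 163.6 / (13.75 × 1.8) = 6.6 kg.
- Largest: 163.6 / (9.56 × 1.0) = 17.1 kg.

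**Step 4. What 1 to 3 kg of water would do, same assumptions.**
- 1 kg: 9.56 × 1.0 to 13.75 × 1.8 = 10 to 25 kcal/day.
- 3 kg: 29 to 74 kcal/day, less than half of the 164.
- As a share of 2413.6: 0.4% to 1.0% for 1 kg and 1.2% to 3.1% for 3 kg, against 6.78%.

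**Step 5. BMI.** For an assumed patient of 70 kg and 1.70 m, 1 kg is 1/70 = 1.4% of weight and 1/1.70² = 0.35 BMI units; 3 kg is 4.3% and 1.04 units. So water alone registers in BMI. These are percentages of weight and cannot be set beside 6.78% of basal metabolism.

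**Step 6. Whether the documents allow a correction.** They give no infusion volume, fluid balance or dry-weight adjustment for any arm, and no BMI or weight value by arm in the visible results.

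**The case against.** **Nutritional status is not read from weight alone.** The screening methods are described as "including questioning patients, using standard anthropometric and laboratory data", and protein and lymphocyte results are reported. Conclusion 1 rests on NRI and SGA. This stands: the point reaches calculated basal metabolism and BMI, and does not overturn the other evidence.

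**The measurement may not have been dropped.** BMI sits beside item 5 in the same plan and did not replace it. Section III.1 presents only some indicators, and a figure and the data that the results refer to are not visible. This also stands. The accurate statement is that item 5 is planned but not specified further, and not reported in the visible text.

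**A reader might infer that intravenous fluid produced the mixed-arm result.** The documents do not support that. They give no volumes by arm, and feeding route does not fix net fluid balance, since enteral feed also supplies water. Extra retained fluid would raise weight and so raise calculated basal metabolism, whereas the mixed arm's value fell. One to three litres would in any case be too little. The passage on exudation and drainage explains protein loss, not weight.

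None of this restores conclusion 3. Its defect follows from the stated equation and needs no fluid hypothesis.

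**Conclusion.** The point holds in this limited form. By the stated definition, the mixed arm's fall of 6.78% (about 164 kcal/day) is a fall in weight of unknown composition. It is not evidence that energy needs were better met, and temperature cannot explain it. Conclusion 3 is therefore unsupported as written.

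This rests on the equation having been used as described, with no undocumented multiplier that varied over time, and on the same patients contributing at both times. If either fails, the fall could come from the multiplier or from a changing set of patients, and it would still not show better coverage. The 6.6 to 17.1 kg range rests on the assumed coefficients and multiplier. A change of that size would itself need to be shown and explained.

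The size and direction of any fluid bias between arms cannot be established from the documents.

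**What to change.** 1. State the method and days of the item 5 measurement, and report fat, water and dry matter by arm and day, together with weight. Interpret BMI and calculated basal metabolism only beside them.
2. If the measurement was not recorded, say so. Withdraw conclusion 3 and any other arm conclusion drawn from postoperative BMI or calculated basal metabolism.
3. Reconcile study plan item 5, section III.1, the basal-metabolism results and Conclusion item 3: whether body composition was measured, whether any factor beyond the four stated inputs entered the calculation, and at what times. The results place the end of feeding at days 10–15 and the Conclusion at days 15–20, while the statistics section compares baseline, day 5 and day 10.

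The cost is a little more analysis of a measurement already planned or, if it was not made, a narrower conclusion. No new data collection is asked for.

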## **1. Methods and procedures.**

At the first stage, modern ideas about methods for assessing nutritional status and methods of nutritional support in the early postoperative period of patients operated on for malignant tumors of the hepatopancreatoduodenal zone were studied.

At the second stage, taking into account the need to select the optimal method of nutritional support in the early postoperative period, patients underwent an intragroup and intergroup comparative analysis of the main clinical and laboratory indicators, reflecting the most satisfactory dynamics of plastic processes regarding the type of nutritional support: enteral, parenteral and mixed.

To solve these problems, a prospective, longitudinal, parallel study and retrospective analysis of the results of treatment of 91 patients with malignant tumors of the hepatopancreatoduodenal zone who underwent the following operations were carried out:

- 1) resection of various segments of the liver;
- 2) hemihepatectomy;
- 3) transhepatic drainage of the right and left hepatic duct;
- 4) bypass gastroenteroanastomosis or cholecystoenteroanastomosis with interintestinal enteroenteroanastomosis according to Brown;
- 5) gastro-pancreatoduodenal resection;
- 6) corporecaudal resection of the pancreas with splenectomy.

The study was carried out on the basis of the KGP at the RVC "Multidisciplinary Hospital No. 3 of the city of Karaganda". Venue: intensive care unit.

To identify nutritional deficiencies, there are screening methods recommended by the international clinical nutrition associations ASPEN (American Society for Parenteral and Enteral Nutrition - ASPEN) and ESPEN (European Society for Parenteral and Enteral Nutrition - ESPEN), including questioning patients, using standard anthropometric and laboratory data, which makes it possible to assess nutritional status and the degree of its impairment.

At the first stage, the clinical condition of the patient was assessed using the Nutritional Risk Screening (NRS, 2002), Subjective Global Assessment (SGA) and Nutritional Risk Index (NRI) protocols before surgery and on the 5th, 10th, 15th day after surgery .

A comparative assessment of the clinical effectiveness of the use of types of nutritional nutrition in a complex of therapeutic measures after these operations in the hepatopancreatoduodenal zone was carried out.

Some nutritional status indicators available for determination at the Oncology Clinic were assessed - body mass index (weight measurements were carried out before surgery, on the 5th, 10th and 15th days), basal metabolic rate (calculated using the Harris-Benedict equation, based on anthropometric data of the patient (gender, age, weight and height).), laboratory parameters: blood hemoglobin, lymphocytes, total protein, serum albumin, serum transferrin, total bilirubin and direct, ALT, AST, which are related to the traditional method for assessing nutritional status.

Additionally, we assessed the duration of postoperative gastostasis, the timing of the onset of intestinal motility, the appearance of stool, the return to a normal diet, the length of patients' stay in the ICU, the readmission of patients to the ICU and the duration of the postoperative bed-day, and the incidence of complications was calculated.

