### **1. Methods for identifying participants and recruiting them.**

The subjects will be selected by a continuous method during screening and patients with cancer pathology will be randomly selected.

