## Report

№ MUK\_NutS-HPD-PO\_2017 from March 17, 2020

Karaganda Medical University

This study was approved by the Karaganda Medical University of the city of Karaganda of the Republic of Kazakhstan. Research and Ethics Committee of February 12, 2020 Protocol №4. All methods were carried out in accordance with ethical principles and rules approved by the ethics committee.

The clinical trial period was started in January 2017 and completed in March 2020

**Purpose of the study:** To improve the nutritional status of cancer patients after operations performed in the hepatopancreatoduodenal zone in connection with malignant neoplasms, through a comprehensive comparative analysis of the effectiveness of isolated enteral, isolated parenteral and mixed type of nutritional support in the early postoperative period.

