## **Methods of statistical data analysis**

All patients hospitalized for special treatment with a verified diagnosis of a malignant neoplasm were subjected to the study in the abdominal department of the KGP at the Regional Oncological Dispensary, Karaganda.

The quantitative and qualitative indicators obtained during the study were analyzed using descriptive and analytical statistics methods. For statistical processing of qualitative (diagnosis codes, dichotomous data) and quantitative variables: symptom intensity, severity, frequency of occurrence, we used the calculation of the median level (Me) with 25%-75% quartiles (Q25; Q75) and the calculation of the arithmetic mean (M) with error (m) and 95% confidence interval (95% CI), standard deviation (s). Quantitative variables were checked for normality of distribution using the Kolmogorov-Smirnov test, as well as the module of Skewness and Kurtosis for quantitative variables  $| \leq 2 |$ . Differences in the 3 groups of patients for quantitative variables corresponding to a normal distribution were identified using the Student's t test for unrelated groups, first for 3 or more groups, and then in pairs for each pair using the Student's t test. Differences for rank variables, or quantitative but not normally distributed for unrelated groups, were determined by the Kruskal-Wallis test or median test for 3 groups, and then pairwise or non-parametric Mann-Whitney test for each of the 3 pairs (groups 1 and 2, groups 1 and 3, groups 2 and 3), and for related groups (dynamic observations) by the Kendall test for 3 groups and then by the Wilcoxon test (Wilcoxon) for each of the 3 pairs (baseline, after 5 days and after 10 days).

Correlation was performed for quantitative variables according to Pearson and for rank variables according to Spearman. Statistical processing of the results was carried out using the Statistica program version 10.

**Results and discussion.** The nutritional status of patients in all three groups before surgery and during the 10-12 days of the postoperative period according to the methods of assessing nutritional status NRS, SGA and NRI was assessed as normal, moderate and severe malnutrition

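### Three feeding groups with no described allocation and an undefined data source are compared by unadjusted tests, yet the report concludes that mixed nutrition is more effective

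*Combined protocol and SAP*

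**What the plan says.** **Design.** The protocol (section III, 1. Methods and procedures) describes "a prospective, longitudinal, parallel study and retrospective analysis of the results of treatment of 91 patients". No section counts patients by source, marks which measurements came from records, or shows source by feeding group. The same section lists six types of operation, from drainage of the hepatic ducts to hemihepatectomy and gastro-pancreatoduodenal resection.

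**Selection.** Section V.1 states: "The subjects will be selected by a continuous method during screening and patients with cancer pathology will be randomly selected". The report (Methods of statistical data analysis) states: "All patients hospitalized for special treatment with a verified diagnosis of a malignant neoplasm were subjected to the study".

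**Groups.** Section II.1 gives the total and the sizes 31, 30 and 30, and defines each group by what it received, for example "The first group (n=31) included patients who received enteral nutrition (EN) after surgery". No section describes an allocation procedure.

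**Analysis.** The protocol (section III, 2. Data analysis and monitoring) names Student's t-test and Pearson correlation. The report adds Kruskal-Wallis or median tests, Mann-Whitney tests, and paired tests over time. None of these carries a covariate.

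**Conclusions.** Conclusion 1 credits mixed nutrition with higher effectiveness than either isolated type. Conclusion 3, and the matching basal-metabolism sentence in Results and discussion, say that it covers patients' energy costs more effectively.

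**Dates.** The Report section states "The clinical trial period was started in January 2017 and completed in March 2020" and cites approval by the "Research and Ethics Committee of February 12, 2020".

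**The concern.** An unadjusted test between groups supports a statement about treatment only if the groups would have had similar outcomes under the same treatment. Random allocation would justify that, but none is described. Without it, the feeding method may follow the operation performed, the patient's condition or the practice of the time, each of which can also affect weight, protein, bilirubin and recovery of the gut. If part of the data came from records, measurement quality may differ as well.

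What is at stake is the main message. A reader of conclusions 1 and 3 would take mixed nutrition to be the cause of the better course. The mention of random selection in section V.1 could reinforce that by being mistaken for randomisation to groups.

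**Working it through.** **1. The stated count.** 31 + 30 + 30 = 91, which agrees with the stated total. It is a head count only: no alpha, power, effect size or SD is given, so it cannot be reproduced as a powered sample size.

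**2. Selection and allocation, side by side.**
- Section V.1: continuous selection at screening and random selection, in one sentence.
- Report, statistical methods: all hospitalised patients with a verified malignancy.
- Route into enteral, parenteral or mixed nutrition: not stated.

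Both rules concern entry to the study. Neither makes the three groups comparable.

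**3. Baseline status.** Numerators are the preoperative SGA-normal counts in Results and discussion. Denominators are the group sizes, assuming every patient was assessed.

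| Group | Normal | Not normal | % normal |
|---|---|---|---|
| Enteral | 24/31 | 7 | 77.4 |
| Parenteral | 19/30 | 11 | 63.3 |
| Mixed | 17/30 | 13 | 56.7 |

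Spread: 77.4 − 56.7 = 20.7 points. For a chi-square test, the overall proportion is 60/91 = 0.659 and the expected normal counts are 20.44, 19.78 and 19.78. Then χ² = (3.56²/20.44 + 0.78²/19.78 + 2.78²/19.78) / (1 − 0.659) = 1.042/0.341 = 3.06. On 2 df, p = exp(−3.06/2) ≈ 0.22.

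Chance could produce this spread, so it does not prove biased allocation. In a non-randomised comparison, however, baseline differences matter whether or not they are significant. The mixed group had 13 patients who could move towards normal and the enteral group had 7. Operation type by group is not reported.

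**4. From analysis to conclusion.** Several results offered for mixed nutrition appear to be changes within a group: total protein p = 0.004 for mixed against 0.108 and 0.129 for the others, and p < 0.03 attached to a fall in basal metabolism in the mixed group. A change that is significant in one group and not in another is not a test of the difference between them. No reported result adjusts for baseline, operation, period or source.

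**5. Dates.** Share of the period before approval = days from start to 12 February 2020 ÷ days from start to end. The start and end days are not given, so both were varied within the stated months.
- Lowest: 31 January 2017 to 31 March 2020, 1107/1155 = 95.8%.
- Highest: 1 January 2017 to 1 March 2020, 1137/1155 = 98.4%.

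Between 18 and 48 days remain after approval.

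**6. Illustration of source confounding (all inputs assumed).** Suppose some patients came from records, their share differs between two groups of 30 by d, and source shifts the outcome by b SD. Then bias = d × b, the standard error of the difference is √(2/30) = 0.258 SD, and the true type I error of a two-sided 5% test is 1 − Φ(1.96 − bias/0.258) + Φ(−1.96 − bias/0.258).

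| d (points) | b = 0.2 SD: bias; error | b = 0.5 SD: bias; error |
|---|---|---|
| 20 | 0.04; 5.3% | 0.10; 6.7% |
| 50 | 0.10; 6.7% | 0.25; 16% |
| 100 | 0.20; 12% | 0.50; 49% |

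The range runs from negligible to severe, and the documents give nothing that places the study within it.

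**The case against.** The design phrase need not mean two sets of patients. A reader might infer that prospective and retrospective patients were pooled, but the text also fits one cohort followed forward whose treatment results were reviewed afterwards. Other parts lean that way: NRS, SGA and NRI were assessed before surgery and on days 5, 10 and 15; the study plan lists record review, consent and tests as steps of one plan; section IV.5 makes written consent a condition of inclusion, and section V.3 requires it from the patient in person. This stands. What can be said is that the data source is undefined.

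A reader might also infer from the late approval that the comparison was chosen after the data were seen. The documents do not show this. Ethics approval is not statistical pre-specification, only one date is reported, and pages were removed before review, so an earlier approval cannot be excluded.

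The selection statements can be partly reconciled: consecutive screening followed by selection, with the report naming the source population. The documents never claim randomisation to groups. Conclusion 3 is worded as a suggestion. These points soften the criticism of the wording, but supply neither an allocation rule nor an adjustment.

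Finally, adjusting for source and period alone would leave operation type and baseline status untouched. That is right, and the fix below includes both.

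**Conclusion.** The point holds as a gap between design and conclusion. The feeding groups have no described allocation, the source of the data is not defined, the operations are heterogeneous and the between-group tests are unadjusted. On that basis the report can describe association; it cannot conclude that mixed nutrition is more effective.

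The one measurable sign of non-comparability is the 20.7-point spread in preoperative SGA-normal status (p ≈ 0.22). It rests on the group sizes as denominators; the report's own later parenteral counts sum to 17 + 14 = 31 against a group size of 30, so they need checking. The size and direction of any bias are unknown. The source-confounding figures are illustrations only, because the source split, the source effect, alpha and power are not given.

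The approval date, after about 96–98% of the stated period, is a discrepancy to be reconciled and is not in itself evidence of bias.

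**What to change.** 1. State how each patient came to a feeding group. Delete the reference to random selection in section V.1 unless a random process existed; if it did, describe it and say what it selected. Reconcile that section with the report's statement that all patients were studied.
2. State whether any patients were taken from records. If so, tabulate source by group and repeat the comparison in prospective patients only.
3. Replace the unadjusted between-group tests with regression on the outcome, adjusted for its baseline value where one exists, operation type and calendar period, plus data source if step 2 applies. Use ANCOVA for continuous outcomes (log scale where skewed, such as bilirubin and transaminases) and logistic or ordinal models for SGA and NRI categories. Name the main comparison, since no primary endpoint is stated. Report differences between groups with confidence intervals, and do not infer them from p-values within groups.
4. Tabulate operation type, enrolment year and baseline SGA by group.
5. Label the comparison non-randomised and exploratory. Limit conclusions 1 and 3, and the matching basal-metabolism sentence in Results and discussion, to association.
6. Reconcile the approval and study dates, or cite any approval that covered enrolment from January 2017.

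**Cost.** A few extra variables per patient, new models, softer conclusions and a modest loss of precision with about 30 per group. A full ANCOVA would use about 13 parameters: intercept 1, group 2, baseline 1, six operations 5, four calendar years 3, source 1. That leaves 91 − 13 = 78 residual degrees of freedom if all patients have data. Sparse operation types or years should be merged by a rule fixed before the reanalysis. Unmeasured reasons for choosing a feeding method would remain, so adjustment does not restore a causal claim.
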